8.2 Sample Size

The total and mixed intrasubject variability CVs (%) observed in study MS200095-0044 for AUC_{0-t} and C_{max} of tepotinib are summarized in Table 5 (total and mixed intra-individual CV for AUC_{0-∞} was very similar to that of AUC_{0-t} and is not listed separately).

Table 5 Overview of the PK-Variability Observed in Tepotinib Study MS200095-0044

Study Part	Formulation (Condition)	Arm	AUC _{0-t}		C _{max}	
			Total Geometric CV%	Mixed intra-individual CV%	Total Geometric CV%	Mixed intra-individual CV%
Part A	TF3 vs TF2 (fasted)	TF3 (fasted)	21.0		22.5	
		TF2 (fasted)	23.4	15.77	20.6	13.94
Part B	TF2 (fed versus fasted)	TF2 (fed)	25.1		19.6	
		TF2 (fasted)	38.1	17.96	29.5	12.67
Part C	TF3 (fed versus fasted)	TF3 (fed)	25.0		17.0	
		TF3 (fasted)	19.8	14.93	15.3	16.79

AUC_{0-t} = area under the plasma concentration-time curve from time zero to the last sampling time at which the concentration is at or above the lower limit of quantification, TF2/3 = tablet formulation 2/3; C_{max} = maximum plasma concentration, CV = coefficient of variation.

Overall, the total variability in AUC and C_{max} was between 15.3% and 25.0% for TF3. The mixed intrasubject variabilities of AUC and C_{max} ranged between 12.67% and 17.96% across all investigated combinations of formulation and condition.

Assuming that the within-subject variability for the comparison between the test and reference treatment will be similar to that of Part A in MS200095-0044 (i.e., CV% = 15.77), and with an assumed geometric mean ratio Test/Reference (GMR T/R) of 0.95, a one-sided alpha level of 0.05, 16 evaluable subjects will be needed to provide approximatively 90% power to show bioequivalence. A drop-out compensation of 2 subjects will be added. In total, 18 subjects will be randomized. If the actual CV is up to 18.4%, the sample size of 16 evaluable subjects would still result in approximately 80% power to show bioequivalence.

8.3 Randomization

Refer to Section 6.3 for the technical and logistical aspects of treatment allocation.

A total of 18 subjects will be randomized. Subjects will be randomized to 1 of 2 sequences at a ratio of 1:1:

Sequence 1: 5 x 100 mg (Test) – 2 x 250mg (Reference)

Sequence 2: 2 x 250 mg (Reference) – 5 x 100 mg (Test)

A computer-generated randomization scheme will be provided by Nuvisan GmbH CTS Department.

8.4 Endpoints

8.4.1 Primary Endpoints

- AUC_{0-t} , $AUC_{0-\infty}$ and C_{max} of tepotinib calculated from concentration data obtained from time zero to 168 h post-dose of each period

8.4.2 Secondary Endpoints

- t_{max} , $t_{1/2}$, apparent total body clearance considering the fraction of dose absorbed (CL/f), and apparent volume of distribution during terminal phase (V_z/f) of tepotinib observed from time zero to 168 h post-dose of each period
- Occurrence of TEAEs (incidence, frequency, intensity and causality), occurrence of changes in safety laboratory assessments, 12-lead ECGs and vital signs.

8.4.3 Exploratory Endpoints

- PK profiles of tepotinib metabolites:

AUC_{0-t} , $AUC_{0-\infty}$, C_{max} , t_{max} , $t_{1/2}$ of tepotinib metabolites observed from time zero to 168 h post-dose of each period

- Genetic variants and mutations in genes that potentially influence PK of tepotinib.

8.5 Analysis Sets

8.5.1 Safety Analysis Set

The Safety analysis set will be defined for each part and will include all subjects who have received at least 1 dose of planned IMP and have had 1 subsequent safety assessment.

8.5.2 Definition of Pharmacokinetic Analysis Set

The PK Analysis Set will include all subjects without any relevant protocol deviations with respect to PK and absence of factors likely to affect the comparability of PK results, with adequate trial medication compliance, and who have valid primary endpoints for both treatments.

All PK analyses will be based on this analysis set.

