8.6 Description of Statistical Analyses

8.6.1 General Considerations

Statistical analyses will be performed using the computer program package SAS® System for Windows™ (Version 9.4 or later; SAS Institute, Cary, North Carolina, USA).

The results of this trial will be reported using summary tables, figures, and data listings, as appropriate. All data will be summarized by treatment and/or scheduled time point, as appropriate.

For demographic, baseline and safety assessments, continuous measurements will be summarized by means of descriptive statistics (ie number and percentage of observations, number and percentage of missing observations, mean, standard deviation [SD], median, 25th and 75th percentiles, minimum, and maximum) and categorical data will be summarized by means of frequency tables (ie count and percentages), if not stated otherwise.

Concentrations of tepotinib and its metabolites in plasma will be presented in tables and descriptively summarized by treatment and nominal time point using n, arithmetic mean, SD, standard error of the mean, median, minimum, maximum, and CV%. Values below the LLOQ will be taken as zero for descriptive statistics of PK concentrations. Descriptive statistics of PK parameters will additionally show the GeoMean, the geometric coefficient of variation (GeoCV%), and the 95% CI for the GeoMean.

Graphical displays will be given, where appropriate. PK variables will be evaluated and listed for all subjects who provide sufficient concentration-time data. Invalid data will be flagged accordingly.

Missing values will be handled as such and not be replaced by estimates.

Details of the statistical analysis will be described in the statistical analysis plan.

Changes in the conduct of the trial or planned analyses, if any, will be reported in the appropriate section of the statistical analysis plan (SAP) and in the clinical trial report.

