8.6.2 Analysis of Primary Endpoints

An analysis of variance (ANOVA) model will be fitted for the log-transformed PK parameters C_{max} , AUC_{0-t} , $AUC_{0-\infty}$ based on the PK analysis set. The model will include treatment, period, sequence as fixed effects and subject within sequence as a random effect.

Treatment differences on the log scale will be estimated for C_{max} , AUC_{0-t} , $AUC_{0-\infty}$ together with their 90% CIs. Point estimates and CIs will be back-transformed to the original scale for the comparisons.

The comparison will be the test treatment (5 x 100 mg TF3) vs the reference treatment (2 x 250 mg TF3) under fasting condition.

The null hypothesis for non-bioequivalence will be rejected if the 90% CI for the ratio of the GeoMean lies within the interval 0.8000 to 1.2500 for all primary pharmacokinetic parameters.

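### One PK Analysis Set, requiring every primary parameter in both periods, governs all PK analyses: valid Cmax and AUC0-t pairs and one-period profiles can leave the analyses for no gain (minor)

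*Protocol*

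**What the plan says.** Section 8.5.2 defines one PK Analysis Set. Besides the absence of relevant deviations and adequate compliance, it requires subjects "who have valid primary endpoints for both treatments". It then fixes the scope: "All PK analyses will be based on this analysis set".

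Section 8.4.1 names three primary endpoints, AUC0-t, AUC0-inf and Cmax, "of tepotinib calculated from concentration data obtained from time zero to 168 h post-dose of each period". Section 8.6.2 fits the three log-scale ANOVAs on this set, with "treatment, period, sequence as fixed effects and subject within sequence as a random effect", and concludes bioequivalence only if each 90% CI "lies within the interval 0.8000 to 1.2500 for all primary pharmacokinetic parameters".

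Section 8.6.1 adds two relevant statements. On missing data: "Missing values will be handled as such and not be replaced by estimates". On what is calculated and listed: "PK variables will be evaluated and listed for all subjects who provide sufficient concentration-time data". Section 7.5.2 repeats the second. No section gives a per-parameter or per-period exception to the set.

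**The concern.** Membership is decided for the subject as a whole, while the data problems arise parameter by parameter and period by period.

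- **Bioequivalence ANOVAs.** Under Section 7.5.2, AUC0-inf needs a terminal regression (the terminal rate constant and the predicted last concentration). Cmax and AUC0-t do not. If the regression is not acceptable in one period, nothing is imputed, the subject fails the set, and observed Cmax and AUC0-t pairs leave their own ANOVAs.
- **Descriptive PK.** The summaries of tmax, half-life, CL/f and Vz/f (Section 8.4.2) and of the metabolites (Section 8.4.3) are descriptive and need no pairing. A subject with one full profile still leaves them. So does a subject whose only failure is the parent drug's AUC0-inf, even for the metabolites.

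At stake are some precision for parameters that have no data problem, and usable descriptive PK in a trial of 18 subjects whose secondary objective is to learn more about tepotinib PK.

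**Working it through.** **Inputs.** From Section 8.2: GMR 0.95, "a one-sided alpha level of 0.05", within-subject CV 15.77% (AUC, Part A of the earlier study), 16 evaluable of 18 randomized, and a sensitivity CV of 18.4%. From Table 5: Cmax CV 13.94% and total CV 21.0% to 23.4% for AUC0-t (both Part A). From Section 5.2.2: mean half-life 30.9 h (95% CI 29.4 to 32.5 h), tmax median 12 h, range 8 to 36 h.

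**Step 1: reproduce the plan's power.** Log-scale SD = sqrt(ln(1 + CV²)); SE = SD × sqrt(½(1/n1 + 1/n2)), which is SD × sqrt(2/N) with balanced sequences; df = N − 2. Power of the two one-sided tests is integrated over the chi-square distribution of the variance estimate. At CV 15.77% and N = 16, SD = 0.1567 and SE = 0.1567 × sqrt(2/16) = 0.0554.

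| CV | N = 14 | N = 15 | N = 16 | N = 18 |
|---|---|---|---|---|
| 13.94% (Cmax) | 92.5% | 94.0% | 95.4% | 97.2% |
| 15.77% (AUC) | 85.8% | 88.1% | 90.2% | 93.3% |
| 18.4% (sensitivity) | 74.1% | 77.3% | 80.4% | 85.1% |

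The stated 90% and 80% at N = 16 both reproduce.

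**Step 2: what the common set costs the decision.** Single-parameter losses, such as 95.4% to 92.5% for Cmax when N falls from 16 to 14, overstate the cost: all three parameters must pass, and AUC0-inf stays at 14 whichever rule is used. The relevant quantity is joint power. It was simulated with GMR 0.95 throughout, CV 15.77% for both AUCs and 13.94% for Cmax, an assumed AUC0-t/AUC0-inf correlation of 0.98, and an assumed AUC/Cmax within-subject correlation of 0.5 to 0.9. With 2 of 16 lacking AUC0-inf:

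- common set (all three parameters on 14): about 80% to 83%;
- per-parameter sets (AUC0-inf on 14, the others on 16): about 82% to 84%.

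The gain is about 1 to 2 points, largest at the lowest correlation.

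**Step 3: how often AUC0-inf should fail.** With mono-exponential decline from time t0, the extrapolated share is exp(−ln 2 × (168 − t0) / half-life). For half-lives of 29.4 to 32.5 h:

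- t0 = 0: 1.9% to 2.8%;
- t0 = 12 h: 2.5% to 3.6%;
- t0 = 36 h: 4.5% to 6.0%.

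If *invalid* meant more than 20% extrapolated (an assumption, taken from the coverage aim of over 80% in Section 5.2.2), the half-life would have to reach ln 2 × 132 / ln 5 = 57 h (t0 = 36 h) or ln 2 × 156 / ln 5 = 67 h (t0 = 12 h). The interval used is a confidence interval for the mean, so individuals vary more, and missing late samples could also spoil the fit. The event should still be uncommon.

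**Step 4: would one-period subjects help the primary test?** Under the random-subject model, with between-subject variance derived from the total CV, adding 2 single-period subjects to 16 complete ones cuts the SE of the treatment contrast by 1.3% to 1.6%. Adding 4 to 14 cuts it by 2.6% to 3.2%. This is negligible.

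**Step 5: descriptive PK.** If both allowed drop-outs complete only one period, 2/18 = 11% of subjects leave the by-treatment summaries.

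**The case against.** The case against has several parts, and much of it stands.

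- **The wording does not literally say all three parameters.** One could read it endpoint by endpoint. But Section 8.5.2 defines a set of subjects, Section 8.4.1 lists three primary endpoints, and a single set serves all three ANOVAs, so the subject-level reading is the plain one. If the other reading was meant, one sentence would settle it.
- **The SAP may handle this.** What counts as *valid* may properly be defined there, and its absence is not held against the protocol. The scope is different: the protocol itself applies the set to all PK analyses, so an SAP with per-parameter inclusion would depart from it.
- **A common set has a virtue.** The three conjunctive tests then rest on the same subjects and the same n. That is true, but it is a matter of presentation.
- **The power scenario is stacked.** Reaching 14 needs both drop-outs and two AUC0-inf failures. With no drop-outs, two failures leave the planned 16. Replacement might also help: Section 5.5.2 allows it for subjects without a full PK dataset, although Section 5.5.1 says drop-outs are not replaced, so this cannot be relied on.

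A reader might also infer more than the document supports:

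- **That the excluded data are thrown away, or that Section 8.6.1 contradicts Section 8.5.2.** Sections 7.5.2 and 8.6.1 keep evaluating and listing those subjects' values; what is lost is their place in the analyses and summaries. Listing everyone while analysing a defined set is ordinary practice.
- **That requiring both periods for the bioequivalence test is wrong.** Complete pairs are a usual choice in a 2×2 crossover, and Step 4 shows that almost nothing is lost.
- **That the trial is underpowered.** The power figures reproduce, and they are stated for evaluable subjects.

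**Conclusion.** The point holds as a minor one. As written, an AUC0-inf failure takes valid Cmax and AUC0-t pairs out of their ANOVAs, and one-period subjects leave descriptive summaries that need no pairing. The first effect is worth about 1 to 2 points of joint power if 2 of 16 subjects are affected. That size depends on the assumed correlations, on GMR 0.95 for every parameter, and on the earlier study's CVs carrying over; allowing for how rarely AUC0-inf should fail, the expected loss is smaller still. The second effect touches up to 11% of subjects in the secondary and metabolite summaries, with their values still listed. Neither effect threatens the validity of the bioequivalence conclusion.

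**What to change.** Replace the scope sentence in Section 8.5.2 with two statements:

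1. Each bioequivalence ANOVA uses every subject who has a valid value of that parameter in both periods and no relevant protocol deviation.
2. Descriptive summaries of secondary and metabolite PK use all subjects with at least one evaluable profile.

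Keep the rule that all three parameters must pass; the type I error argument is unaffected. The cost is two sentences. The one downside is that n may differ between parameters and between treatments, so it must be shown in each table. The change should be made before any concentration data are available, so that membership of the primary analysis is not argued afterwards.

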8.6 Description of Statistical Analyses

8.6.1 General Considerations

Statistical analyses will be performed using the computer program package SAS® System for Windows™ (Version 9.4 or later; SAS Institute, Cary, North Carolina, USA).

The results of this trial will be reported using summary tables, figures, and data listings, as appropriate. All data will be summarized by treatment and/or scheduled time point, as appropriate.

For demographic, baseline and safety assessments, continuous measurements will be summarized by means of descriptive statistics (ie number and percentage of observations, number and percentage of missing observations, mean, standard deviation [SD], median, 25th and 75th percentiles, minimum, and maximum) and categorical data will be summarized by means of frequency tables (ie count and percentages), if not stated otherwise.

Concentrations of tepotinib and its metabolites in plasma will be presented in tables and descriptively summarized by treatment and nominal time point using n, arithmetic mean, SD, standard error of the mean, median, minimum, maximum, and CV%. Values below the LLOQ will be taken as zero for descriptive statistics of PK concentrations. Descriptive statistics of PK parameters will additionally show the GeoMean, the geometric coefficient of variation (GeoCV%), and the 95% CI for the GeoMean.

Graphical displays will be given, where appropriate. PK variables will be evaluated and listed for all subjects who provide sufficient concentration-time data. Invalid data will be flagged accordingly.

Missing values will be handled as such and not be replaced by estimates.

Details of the statistical analysis will be described in the statistical analysis plan.

Changes in the conduct of the trial or planned analyses, if any, will be reported in the appropriate section of the statistical analysis plan (SAP) and in the clinical trial report.

8.6.2 Analysis of Primary Endpoints

An analysis of variance (ANOVA) model will be fitted for the log-transformed PK parameters C_{max} , AUC_{0-t} , $AUC_{0-\infty}$ based on the PK analysis set. The model will include treatment, period, sequence as fixed effects and subject within sequence as a random effect.

Treatment differences on the log scale will be estimated for C_{max} , AUC_{0-t} , $AUC_{0-\infty}$ together with their 90% CIs. Point estimates and CIs will be back-transformed to the original scale for the comparisons.

The comparison will be the test treatment (5 x 100 mg TF3) vs the reference treatment (2 x 250 mg TF3) under fasting condition.

The null hypothesis for non-bioequivalence will be rejected if the 90% CI for the ratio of the GeoMean lies within the interval 0.8000 to 1.2500 for all primary pharmacokinetic parameters.

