- Tepotinib film-coated tablet TF3 containing 100 mg of drug substance for oral administration (test treatment)
- Tepotinib film-coated tablet TF3 containing 250 mg of drug substance for oral administration (reference treatment)

Administration of single doses of 500 mg tepotinib per treatment period, administered as 2 tablets of 250 mg, and 5 tablets of 100 mg, after overnight fasting.

The washout period between single doses will be at least 21 days.

Reference therapy: dose/mode of administration/dosing schedule: Not applicable**Planned trial and treatment duration per subject:**

About 9 weeks each from Screening to End of Trial Visit, including 2 treatment periods of 21 days each.

Statistical methods:**Primary Endpoints:**

An analysis of variance (ANOVA) model will be fitted to the log-transformed PK parameters C_{max} , AUC_{0-t} , $AUC_{0-\infty}$ based on the PK analysis set. The model will include treatment, period, sequence as fixed effects and subject within sequence as random effect.

Treatment differences on the log scale of tepotinib will be estimated for C_{max} , AUC_{0-t} , $AUC_{0-\infty}$ together with their 90% CIs.

The null hypothesis of non-bioequivalence will be rejected if the 90% CI for the ratio of the geometric mean lies within the bioequivalence acceptance interval of 0.8000 to 1.2500 for all primary PK parameters.

Secondary and exploratory endpoints will be analyzed with summary statistics.

Table 1 **Schedule of Assessments**

Assessment/ Activity	Screening	All periods				End of Trial Visit
Day	-21 to -2	-1	1	2 - 4	5 - 8	21 (± 1) after dosing in Period 2
Written informed consent ^a						
Hospitalization		X -----		X		
Ambulatory visits	X				X	X
In-/exclusion criteria	X	X (Period 1 only)				
Randomization			X (predose, Period 1 only)			
Demographic data (incl. height, weight, BMI)	X					
Medical history	X					
Physical examination	X	X		Day 2, Day 4 ^e		X
Vital signs (blood pressure, pulse rate, body temperature)	X	X	pre-dose, 2 h, 8 h	Day 2, Day 4 ^e		X
12-lead safety ECG	X	X	pre-dose ^b , 2 h, 8 h	Day 2, Day 4 ^e		X
Clinical laboratory (hematology, biochemistry, urinalysis)	X	X	pre-dose	Day 2, Day 4 ^e		X
Coagulation	X					
Serology (HIV/hepatitis)	X					
Pregnancy test (in serum at Screening and End of Trial Visit, in urine on Day -1)	X	X				X
Urine drug screen; Alcohol breath test	X	X				
Administration of tepotinib			X			
PK blood sampling			X ^c	X ^c	X ^c	
PGx blood sampling		X (Period 1 only)				

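### With complete pairs only, the random subject term in the primary model gains nothing and, under a bounded likelihood fit, could lift the one-sided error slightly above 5%; a fixed subject term removes this at no cost

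*Protocol*

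**What the plan says.** Section 8.6.2 fits an ANOVA to log Cmax, AUC0-t and AUC0-∞: "The model will include treatment, period, sequence as fixed effects and subject within sequence as a random effect". The statistical methods part of the synopsis says the same: "The model will include treatment, period, sequence as fixed effects and subject within sequence as random effect". Neither place names an estimation method, a bound on the variance component or a degrees-of-freedom rule. Section 8.6.1 leaves analysis details to the SAP.

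Section 8.5.2 admits to the PK Analysis Set only subjects "who have valid primary endpoints for both treatments", and adds: "All PK analyses will be based on this analysis set". A subject with one usable period therefore cannot contribute.

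Section 8.2 plans on an intra-individual CV of 15.77%, taken from Part A of study MS200095-0044, and a ratio of 0.95: "a one-sided alpha level of 0.05, 16 evaluable subjects will be needed to provide approximatively 90% power to show bioequivalence". It also gives about 80% power if the CV is 18.4%. Table 5 lists total and intra-individual CVs for the three parts of that study. The intra-individual values "ranged between 12.67% and 17.96% across all investigated combinations of formulation and condition".

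**The concern.** In a two-period crossover, a random subject effect is useful when some subjects contribute one period only, because it recovers between-subject information on the treatment contrast. With complete pairs there is none to recover. The estimate and its standard error equal those from a fixed subject effect whenever the between-subject variance is estimated as positive.

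The two differ when that variance is estimated as zero under a non-negativity bound. The fit then drops the subject term and pools the two mean squares. It does so only in trials where the between-subject mean square is the smaller, so pooling always lowers the error variance. Taken over all trials, the 90% CI then covers less than 90%, and the one-sided 5% level in 8.2 is no longer exact. All three parameters must pass, so the trial's error is affected only if the affected parameter is the limiting one.

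**Working it through.** **1. The plan's own power.** Inputs from 8.2: CV 15.77%, ratio 0.95, n = 16, one-sided 0.05. Within-subject log variance: σw² = ln(1 + 0.1577²) = 0.02457. Standard error of the treatment difference: √(2 × 0.02457/16) = 0.0554, on n - 2 = 14 df. Exact power of the two one-sided tests is 90.2%. At CV 18.4% it is 80.4%. Both stated figures are reproduced, on the within-subject interval with n - 2 df.

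**2. What a bounded fit does.** With 16 complete pairs in two sequences, the within-subject mean square (MSW) and the between-subject mean square (MSB) each have 14 df. Their expectations are σw² and σw² + 2σb². The estimate of σb² is (MSB - MSW)/2, set to zero if MSB < MSW. In that case the error variance becomes (14 MSB + 14 MSW)/28, used with 14 or 28 df depending on the df method. Fixed-effect and REML fits to simulated paired data agree with this. Standard errors were identical when the variance estimate was positive. When it was zero the REML standard error was smaller (for example 0.0587 against 0.0617), with the same point estimate.

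**3. What Table 5 implies.** Total log variance is the mean of ln(1 + CV²) over the two arms. Within-subject variance is ln(1 + CV²) of the intra-individual CV. Between-subject variance is the difference, taken before rounding, and the intraclass correlation (ICC) is between/total. The last column is P(F(14,14) < MSW/MSB) for n = 16.

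| Cell | Total | Within | Between | ICC | P(estimate = 0) |
|---|---|---|---|---|---|
| Part A AUC | 0.04823 | 0.02457 | 0.02367 | 0.49 | 2.7% |
| Part A Cmax | 0.04547 | 0.01925 | 0.02623 | 0.58 | 1.0% |
| Part B AUC | 0.09832 | 0.03175 | 0.06657 | 0.68 | 0.2% |
| Part B Cmax | 0.06057 | 0.01593 | 0.04465 | 0.74 | 0.06% |
| Part C AUC | 0.04954 | 0.02205 | 0.02749 | 0.55 | 1.3% |
| Part C Cmax | 0.02581 | 0.02780 | -0.00199 | -0.08 | 50% (true variance set to 0) |

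Allowing for rounding of the CVs, the Part C Cmax value lies between about -0.0022 and -0.0018.

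**4. Size of the effect.** Simulation of 2,000,000 trials per setting, n = 16, true ratio on an acceptance limit (0.80 and 1.25 are symmetric on the log scale):

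| Setting | Fixed subject | Bounded, 14 df | Bounded, 28 df |
|---|---|---|---|
| ICC 0, CV 15.77% | 5.0% | 5.6% | 5.9% |
| ICC 0.2, CV 15.77% | 5.0% | 5.2% | 5.3% |
| Part A AUC (ICC 0.49) | 5.0% | 5.0% | 5.0% |
| Part A Cmax (ICC 0.58) | 5.0% | 5.0% | 5.0% |

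The bound is reached in 50% of trials at ICC 0 and in 23% at ICC 0.2. At ICC 0, overall coverage of the 90% CI is 90.0% with a fixed subject effect, 88.8% bounded with 14 df and 88.3% bounded with 28 df.

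**5. Where the coverage is lost.** At ICC 0, in the trials with a zero estimate, the bounded interval is on average 9% (14 df) or 12% (28 df) narrower than the fixed-effect one, yet it still covers 91.1% or 90.0%. The fixed-effect interval covers 93.5% in those trials, because MSW tends to be large there. In the other half both methods agree and cover about 2 × 90.0 - 93.5 = 86.5%. Pooling removes the over-coverage that balances that half: (91.1 + 86.5)/2 = 88.8% and (90.0 + 86.5)/2 ≈ 88.3%.

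**The case against.** The strongest case against acting is that the protocol states nothing wrong. It says ANOVA. A moment ANOVA with a random subject term gives the fixed-effect interval exactly, and the SAP, which is not shown, may settle the estimator and the df. That stands: the inflation depends on an assumed bounded likelihood fit that the protocol does not prescribe. What remains is that the random term is stated in the protocol itself and has no benefit for the analysis set the protocol defines.

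Two stronger readings are tempting, and neither is supported. A reader might infer that the CI is too narrow whenever the between-subject variance is estimated as zero. Step 5 shows that those intervals still cover 90% or more; the loss belongs to the procedure over all trials.

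A reader might also infer from Table 5 that a zero variance is to be expected for Cmax of TF3. One cell of six points that way. Part C is the only part with TF3 in both arms, but it compares fed with fasted, and its number of subjects is not given, so the precision of -0.002 cannot be judged. Part A, a fasted formulation comparison and the protocol's planning basis, gives an ICC of 0.58 for Cmax. Averaging the Part A and Part C variance components for Cmax gives an ICC of 0.34, where the error is about 5.1% at most.

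**Conclusion.** The point holds as a small, free improvement and not as an error in the plan. For complete pairs the random subject term has no advantage over a fixed one. The possible cost is an overall one-sided error of at most about 5.6% (14 df) or 5.9% (28 df) instead of 5.0%. Reaching it requires three things together: a likelihood fit with a non-negativity bound, a true between-subject variance of zero, and the affected parameter being the one that limits the bioequivalence decision. At the Part A variances the error is 5.0%. The documents therefore do not support saying that the trial's type I error is uncontrolled, nor do they put the power claim in doubt; both power figures are reproduced.

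**What to change.** In 8.6.2 and in the statistical methods of the synopsis, state subject within sequence as a fixed effect. Alternatively, keep it random and state that the variance component is unconstrained (negative estimates allowed) with n-2 df. For complete pairs both give the exact within-subject t interval, whatever the between-subject variance. The unconstrained random version would also serve if one-period data were ever admitted.

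The cost is one phrase in two places and one setting in the analysis program. No planned power is lost, because the 90.2% and 80.4% in step 1 already rest on this interval. At zero between-subject variance, CV 16.79% and ratio 0.95, a bounded fit would show 88.9% (14 df) or 89.5% (28 df) power against 86.7% with a fixed subject effect, but that gain comes with the excess error.
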